6.4 STUDY INTERVENTION/EXPERIMENTAL MANIPULATION ADHERENCE

Not applicable

6.5 CONCOMITANT THERAPY

Not applicable

6.5.1 RESCUE THERAPY

Not applicable

7 STUDY INTERVENTION/EXPERIMENTAL MANIPULATION DISCONTINUATION AND PARTICIPANT DISCONTINUATION/WITHDRAWAL

7.1 DISCONTINUATION OF STUDY INTERVENTION/EXPERIMENTAL MANIPULATION

Not applicable

7.2 PARTICIPANT DISCONTINUATION/WITHDRAWAL FROM THE STUDY

Not applicable

7.3 LOST TO FOLLOW-UP

Not applicable

8 STUDY ASSESSMENTS AND PROCEDURES

8.1 ENDPOINT AND OTHER NON-SAFETY ASSESSMENTS

Data will be obtained by providing CURES with a list of prescriber names, alongside randomized digit IDs to anonymize human subjects. The list will include the date range for retrieving all schedule II, III, and IV drugs written by the prescriber in that time. These dates will be based on the decedent date of death and letter sent date for each prescriber - 12 months before the decedent date of death and 13 months after the letter was sent, which includes a one-month wash out period. Based on the earliest decedent date of death and latest letter sent date, we will obtain data from October 1, 2017 to August 31, 2021. CURES will provide the data to USC researchers with the randomized digit IDs (i.e., omitting prescriber and patient names) to ensure the confidentiality and privacy of human subjects. All data will be transferred and reintegrated into LA Medical Examiner-Coroner's database using Secure File Transfer Protocol.

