1.2 SCHEMA

1.3 SCHEDULE OF ACTIVITIES

Assessment	Enrollment	Randomization	Baseline	Intervention Period	Observation Period	Follow-up Period
	January 2019 to July 2020	Monthly: 12 months prior April 2019 to to decedent July 2020 date of death (DOD)		1-6 months after DOD	2-13 months after Letter is sent	> 13 months after letter is sent
Data attainment on demographics	X	X	X			
Inclusion/Exclusion Criteria	X					
Data attainment on controlled substances			X	X	X	
Data analysis						X

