5.1 INCLUSION CRITERIA

The inclusion criteria for clinicians are as follows: a) must be located in Los Angeles County, b) have scheduled drug prescribing privileges and, c) have prescribed a schedule II, III, or IV drug to a person in the 12 months prior to their opioid-related death.

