9 STATISTICAL CONSIDERATIONS

9.1 STATISTICAL HYPOTHESES

Milligram morphine equivalents in prescriptions filled daily by patients of letter recipients will decrease following receipt of letter as compared to baseline.

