9.4.4 SAFETY ANALYSES

Although we will be unable to determine if there are hospitalizations or ED visits for opioid withdrawal in patients of clinicians in the intervention group, we will monitor this potential safety issue by comparing clinicians who received a letter to controls to determine if there are any dramatic reductions (>20% from baseline) in opioid prescribing in the post-intervention period as a result of the letter. The U.S. does not have an integrated healthcare system with complete data on hospitalizations for all patients to evaluate induced withdrawal. However, it is possible for us to evaluate if providers induce withdrawal on patients by exhibiting high rates of MME reductions (see p. 589 Doctor et al., Science 361, 588–590 (2018)). In our previous work, we demonstrated that for letters, there was no difference in the proportion of prescribers in the intervention or control group who made substantial (>20%) reductions in opioid prescribing in the post-intervention period ($z = 1.279$, $P > 0.05$). We will use this same outcome to evaluate potential harm to patients in this trial.

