10.1.9 DATA HANDLING AND RECORD KEEPING

10.1.9.1 DATA COLLECTION AND MANAGEMENT RESPONSIBILITIES

Decedent data is collected from hard copies of death reports at the LA County office. Prescriber data is collected electronically from the CURES online portal, CURES Research Center, and the CA Department of Consumer Affairs (DCA) website. Patient and physician data are recorded in a secure, electronic database, and maintained by study analysts.

CURES provides records of opioids dispensed at California pharmacies attributable to each provider in our sample treating all civilian, non-Veteran's Administration and non-institutionalized patients. The Medical Examiner has authority to use CURES for the purpose of educating practitioners and others in lieu of disciplinary, civil, or criminal actions, in accordance with the California State's Health and Safety Code § 11165(c)(2). First name, last name, date of birth and address will identify each decedent in the medical examiner reports and CURES data. Drug Enforcement Agency (DEA) number will identify the prescribers in CURES data. Data from eligible clinicians will be extracted from CURES and kept onsite (Windows 10 OS) at the medical examiner's office for de-identified analytic file preparation. A file stripped of patient and clinician identifiers will be prepared and released for analysis on secure servers at the University of Southern California.

Data will be entered, tracked, edited, updated and reported by pre-approved analysts with the appropriate clearance.

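### The baseline year contains the index decedent's own fills and follow-up cannot, which biases the pre-post fall in 9.1 towards benefit and inflates the absolute >20% reduction rate, but does not bias letter A versus letter B

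*Combined protocol and SAP*

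**What the plan says.** Section 5.1(c) requires a clinician to "have prescribed a schedule II, III, or IV drug to a person in the 12 months prior to their opioid-related death". Section 8.1 sets the data windows at "12 months before the decedent date of death and 13 months after the letter was sent, which includes a one-month wash out period", and within them calls for "retrieving all schedule II, III, and IV drugs written by the prescriber in that time". The schedule in 1.3 places the intervention "1-6 months after DOD", so the whole follow-up year lies after the death.

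The one hypothesis, in 9.1, is that MME among letter recipients "will decrease following receipt of letter as compared to baseline". The estimator in 9.4.1 is different: it compares the change over time under letter A with the change under letter B. Sections 8.2 and 9.4.4 add a safety comparison of letter recipients with controls to "determine if there are any dramatic reductions (>20% from baseline) in opioid prescribing in the post-intervention period". Section 8.3.4 commits staff to investigate every case that the safety measures identify, with manual chart review.

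None of 8.1, 8.2, 9.4.1, 9.4.4 or 10.1.9.1 excludes the decedent's prescriptions from any of these quantities.

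**The concern.** The entry criterion guarantees that baseline holds at least one scheduled-drug prescription to a person who is dead throughout follow-up. If that drug was an opioid, the prescriber's MME tends to fall because the patient died, whatever the letter did. If it was a benzodiazepine, the same applies to BE.

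Two results are exposed. The first is any fall from baseline, which is what 9.1 hypothesises. Everyone in this trial receives a letter, so no unlettered group shows how much of the fall would have happened anyway. The second is the share of prescribers with a >20% reduction. That measure is meant to detect abrupt withdrawal of opioids from living patients, but it would also count prescribers whose total dropped because the index patient had died.

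**Working it through.** The plan gives no figure for the decedent's contribution, so there is nothing of its own to reproduce. The sample size in 9.2 does not enter this check.

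1. **Timing.** Baseline is the 12 months ending at death (8.1). The letter goes out 1 to 6 months after death (1.3), and the analysed year is months 2 to 13 after the letter. The decedent can contribute to baseline only.

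2. **Effect on the 20% line.** Let s be the decedent's share of the prescriber's baseline MME. If the remaining patients' MME falls by a fraction r, the post/baseline ratio is (1 − s)(1 − r). The line is reached when r = 1 − 0.8/(1 − s):
   - s = 5%: r = 15.8%
   - s = 10%: r = 11.1%
   - s = 15%: r = 5.9%
   - s = 20%: r = 0

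   The death alone triggers the flag only when s exceeds 20%, for example when the decedent was one of four equal-dose opioid patients (s = 25%).

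3. **What s might be.** The documents do not say. For illustration, take the earlier trial's letter-arm baseline of 72.5 (2.1) as mean daily MME per prescriber, which is an assumption. Then 20% is 14.5 MME/day, or 14.5 × 365 ≈ 5,290 MME a year. That corresponds to one patient at 50 MME/day for 106 days, or at 90 MME/day for 59 days, all from one prescriber. With share = (dose × days/365)/72.5, and doses and days assumed:
   - 20 MME × 7 days: 0.5%
   - 50 MME × 30 days: 5.7%
   - 50 MME × 90 days: 17.0%
   - 50 MME × 180 days: 34.0%

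   Split evenly over the mean of 5.5 prescribers per decedent (9.2), these become 0.1%, 1.0%, 3.1% and 6.2%. Volume matters as well: 50 MME × 180 days from one prescriber is 12.3% of a 200 MME/day baseline and 4.9% of a 500 MME/day baseline.

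4. **Absolute flag rate.** Suppose the year-to-year change in ln(MME) among the other patients is normal with mean zero. The chance of a flag with no change in behaviour is Φ((ln 0.8 − ln(1 − s))/SD). The SD is assumed, so two values are shown for s = 0, 5%, 10% and 15%:
   - SD 0.3: 22.8%, 28.3%, 34.7%, 42.0%
   - SD 0.6: 35.5%, 38.7%, 42.2%, 46.0%

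5. **Between-arm flag comparison.** In the same model at SD 0.3, give one arm an extra real fall of 5%. At s = 0 the rates are 22.8% and 28.3%, a difference of 5.5 points. At s = 10% they are 34.7% and 41.2%, a difference of 6.5 points. Dividing by √(p₁(1 − p₁) + p₂(1 − p₂)) gives standardised differences of 0.089 and 0.095. If s varies between prescribers (skewed beta distributions with mean 10%, assumed), the figure is 0.082 to 0.089.

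6. **Primary contrast.** Decedents are randomised to A or B (4.1, 6.3), so s has the same distribution in both arms in expectation. The expected bias in the A-versus-B difference in differences is zero.

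**The case against.** The strongest reply is that the analysis in 9.4.1 and any between-arm safety comparison are protected by randomisation. This stands. A reader might infer that the artefact hides a real difference in safety between the letters. Step 5 does not support that: detectability is about unchanged, with at most a slight loss when s varies.

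A reader might also infer that every prescriber's MME falls. The documents do not support this. Entry is on any schedule II, III or IV drug, and one stratum in 4.1 is benzodiazepine-only deaths. A prescriber who gave the decedent no opioid loses no MME, and one who wrote a single short prescription loses very little.

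The chart review in 8.3.4, which includes a judgement of relatedness, could recognise a fall that the decedent's absence explains. This also stands in part: the cost is then unnecessary reviews rather than an unnoticed false signal. The published absolute rate would still be too high.

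Finally, the earlier trial's control arm moved by only +0.1 (71.6 to 71.7, section 2.1), which shows no average fall. This is weak counter-evidence. The documents do not say whether that baseline contained decedents' fills, and its follow-up was 3 months rather than 12.

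**Conclusion.** The point holds in a limited form. The decedent's fills are in baseline by selection, are absent from follow-up by necessity, and are nowhere removed. The pre-post fall in 9.1 is therefore biased towards benefit, and the absolute >20% rate is inflated wherever the decedent was a material share of a prescriber's MME. The A-versus-B estimate is not biased; varying shares only add some noise to each prescriber's change.

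The size cannot be fixed from the documents, because the distribution of s is not given. The calculations above also assume that the lost patient's volume is not replaced by new patients.

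It is tempting to say that a mean share of 5% would imitate the whole effect assumed in 9.2, since half of the earlier 9.7% is about 5%. That is not shown. The share s refers to annual total MME, whereas 9.4.1 models log MME on dispensing days with zero-dispensing days censored, so a 5% share need not appear as 5% on that scale. This is a worthwhile, inexpensive improvement and not a threat to the randomised comparison.

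**What to change.** In 8.1, 9.4.1 and 9.4.4, state that fills dispensed to study decedents who died before that prescriber's letter was sent are excluded from MME, BE and the >20% measure in all windows. Limiting the rule to deaths before the letter avoids conditioning on later deaths, which the letter could affect. It also covers prescribers linked to more than one decedent.

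The flag must be set before identifiers are removed. Section 10.1.9.1 makes this feasible: "First name, last name, date of birth and address will identify each decedent in the medical examiner reports and CURES data", and it has the analytic file prepared at the medical examiner's office. Section 8.1, however, has CURES sending data to the university researchers while "omitting prescriber and patient names". The two data routes should be reconciled. If the data go directly to the analysts, CURES would have to set the flag.

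Prescribers left with zero baseline opioid MME have no defined percentage reduction. Keep them in the MME and BE models, take them out of the denominator of the >20% measure, and report their number by arm. Report results including the decedents' fills as a sensitivity analysis.

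The cost is one extra data-preparation step and a slightly smaller safety denominator. No new data are collected.

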8.2 SAFETY ASSESSMENTS

Although we will be unable to determine if there are hospitalizations or ED visits for opioid withdrawal in patients of clinicians in the intervention group, we will monitor this potential safety issue by comparing clinicians who received a letter to controls to determine if there are any dramatic reductions (>20% from baseline) in opioid prescribing in the post-intervention period as a result of the letter. The U.S. does not have an integrated healthcare system with complete data on hospitalizations for all patients to evaluate induced withdrawal. However, it is possible for us to evaluate if providers induce withdrawal on patients by exhibiting high rates of MME reductions (see p. 589 Doctor et al., *Science* 361, 588–590 (2018)). In our previous work, we demonstrated that for letters, there was no difference in the proportion of prescribers in the intervention or control group who made substantial (>20%)

reductions in opioid prescribing in the post-intervention period ($z = 1.279$, $P > 0.05$). We will use this same outcome to evaluate potential harm to patients in this trial.

8.3 ADVERSE EVENTS AND SERIOUS ADVERSE EVENTS

8.3.1 DEFINITION OF ADVERSE EVENTS

This protocol uses the definition of adverse event from 21 CFR 312.32 (a): any untoward medical occurrence associated with the use of an intervention in humans, ***whether or not considered intervention-related.***

8.3.2 DEFINITION OF SERIOUS ADVERSE EVENTS

Not applicable

8.3.3 CLASSIFICATION OF AN ADVERSE EVENT

8.3.3.1 SEVERITY OF EVENT

For adverse events (AEs) not included in the protocol defined grading system, the following guidelines will be used to describe severity.

- **Mild** – Events require minimal or no treatment and do not interfere with the participant's daily activities.
- **Moderate** – Events result in a low level of inconvenience or concern with the therapeutic measures. Moderate events may cause some interference with functioning.
- **Severe** – Events interrupt a participant's usual daily activity and may require systemic drug therapy or other treatment. Severe events are usually potentially life-threatening or incapacitating. Of note, the term "severe" does not necessarily equate to "serious".]

8.3.3.2 RELATIONSHIP TO STUDY INTERVENTION/EXPERIMENTAL MANIPULATION

All adverse events (AEs) will have their relationship to study procedures, including the intervention, assessed by an appropriately-trained clinician based on temporal relationship and his/her clinical judgment. The degree of certainty about causality will be graded using the categories below.

- **Related** – The AE is known to occur with the study procedures, there is a reasonable possibility that the study procedures caused the AE, or there is a temporal relationship between the study procedures and the event. Reasonable possibility means that there is evidence to suggest a causal relationship between the study procedures and the AE.
- **Not Related** – There is not a reasonable possibility that the study procedures caused the event, there is no temporal relationship between the study procedures and event onset, or an alternate etiology has been established.

OR

- **Definitely Related** – There is clear evidence to suggest a causal relationship, and other possible contributing factors can be ruled out. The clinical event, including an abnormal laboratory test result, occurs in a plausible time relationship to study procedures administration and cannot be explained by concurrent disease or other drugs or chemicals. The response to withdrawal of the study procedures should be clinically plausible. The event must be pharmacologically or phenomenologically definitive.
- **Probably Related** – There is evidence to suggest a causal relationship, and the influence of other factors is unlikely. The clinical event, including an abnormal laboratory test result, occurs within a reasonable time after administration of the study procedures, is unlikely to be attributed to concurrent disease or other drugs or chemicals, and follows a clinically reasonable response on withdrawal.
- **Potentially Related** – There is some evidence to suggest a causal relationship (e.g., the event occurred within a reasonable time after administration of study procedures). However, other factors may have contributed to the event (e.g., the participant's clinical condition, other concomitant events). Although an AE may rate only as "possibly related" soon after discovery, it can be flagged as requiring more information and later be upgraded to "probably related" or "definitely related", as appropriate.
- **Unlikely to be related** – A clinical event, including an abnormal laboratory test result, whose temporal relationship to study procedures administration makes a causal relationship improbable (e.g., the event did not occur within a reasonable time after administration of the study procedures) and in which other drugs or chemicals or underlying disease provides plausible explanations (e.g., the participant's clinical condition, other concomitant treatments).
- **Not Related** – The AE is completely independent of study procedures administration, and/or evidence exists that the event is definitely related to another etiology. There must be an alternative, definitive etiology documented by the clinician.]

8.3.3.3 EXPECTEDNESS

An AE will be considered unexpected if the nature, severity, or frequency of the event is not consistent with the risk information previously described for the study procedures.

Although we will be unable to determine if there are hospitalizations or ED visits for opioid withdrawal in patients of clinicians in the intervention group, we will monitor this potential safety issue by comparing clinicians who received a letter to controls to determine if there are any dramatic reductions (>20% from baseline) in opioid prescribing in the post-intervention period as a result of the letter. The U.S. does not have an integrated healthcare system with complete data on hospitalizations for all patients to evaluate induced withdrawal. However, it is possible for us to evaluate if providers induce withdrawal in patients by exhibiting high rates of MME reductions (see p. 589 Doctor et al., *Science* 361, 588–590 (2018)). In our previous work, we demonstrated that for letters, there was no difference in the proportion of prescribers in the intervention or control group who made substantial (>20%) reductions in opioid prescribing in the post-intervention period ($z = 1.279$, $P > 0.05$). We will use this same outcome to evaluate potential harm to patients in this trial.

8.3.4 TIME PERIOD AND FREQUENCY FOR EVENT ASSESSMENT AND FOLLOW-UP

At any time, clinicians can report an adverse event or unanticipated problem potentially related to the letters to the medical examiner's office or the County or City public health officer who co-signs the letter and provides contact information.

We do not expect there to be adverse events directly influenced by the clinical guidance being delivered in this study. All study interventions encourage clinicians to follow well-established national guideline recommendations and known best practices. While the expectedness of adverse events is very low, we will investigate each and every numerator case identified in all safety measures described above. For cases identified by the safety monitoring measures, we will perform manual physician chart review to examine the clinical circumstances and to make a judgment (1) the expectedness of the event [unexpected, expected], (2) the likelihood that the safety event was study related [not related/possibly related/definitely related] and (3) judge the event's severity [abnormal clinical finding without symptoms/symptoms requiring clinical intervention/short term disability or hospitalization/death AND separately define the severity as mild, moderate, or severe].

These will be conducted only by authorized study personnel. Study personnel will interview clinicians treating patients when needed to obtain additional information. Each case identified will have a case report form with these variables and will be signed and dated by study staff completing the form. These forms will be stored in a locked office. Each adverse event will be given an identification number. If study personnel believe that a patient that experienced an adverse event would benefit from seeing or communicating with their clinician who previously received a letter, the PI will within 2 business days reach out to this clinician advising them to contact the patient as soon as possible.

We will within a business day report any clinician reported adverse events, safety analysis, or unanticipated problems to the USC IRB. Our report will include appropriate identifying information for the study, a detailed description of the adverse event, and a description of any changes to the protocol or other corrective actions that have been taken or are proposed. If an adverse event occurs, we will review relevant clinical decision support and ensure others are not at a greater risk of harm than was previously known or recognized. We will notify our NIA Program Officer of any serious adverse events.

Clinician participants are only receiving a letter informing them of a recent patient death due to opioid overdose. Additional patient deaths related to this study are not expected. However, should we identify a patient death in safety measures described above we will report the death to the NIA Program Officer and the USC IRB within 24 hours of our knowledge of the death.

The seriousness of the adverse event will be documented on the case report form. We will categorize all of the following as serious adverse events: patient death, life-threatening event, hospitalization-initial or prolonged, disability/incapacity, and events that required intervention to prevent permanent impairment. The clinician reviewing the event will determine the seriousness of the event. If it is an event other than those listed above that the reviewing clinician feels is an 'other' serious event, it will be discussed with another clinical study team member to reach consensus. All details will be documented on a case report form.

